14.1 Best Overall Response

Best overall response (BOR) will be assessed based on the tumor response at different evaluation time points from baseline until the first documented disease progression. The unconfirmed BOR will be defined by the best overall response reached by the participant during this period, while the confirmed BOR will have to meet additional rules of confirmation as defined in the following sections. Only tumor assessments performed before the start of any further anticancer treatment will be considered in the assessment of BOR. Clinical deterioration will not be considered as documented disease progression.

Objective Response (OR) is defined as complete response (CR) or partial response (PR) according to evaluation criteria from start date until documented disease progression. Patients who do not have an on-treatment radiographic tumor assessment due to early progression, who receive anti-tumor treatments other than the study treatments prior to reaching a CR or PR, or who die, progress, or drop out for any reason prior to reaching a CR or PR will be counted as non-responders in the assessment of OR. Each patient will have an objective response status (0: no OR; 1: OR). OR rate (ORR) is the proportion of patients with OR in the analysis set.

Disease Control Rate (DCR) is defined as the proportion of participants with BOR according to evaluation criteria of CR, PR, or SD. For RECIST 1.1 as adjudicated by IRC, non-CR/non-PD will also be considered in DCR evaluation.

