8.3.2 Secondary Endpoints

[figure not shown]
The secondary endpoints for the dose escalation part of the trial are:

- MSB0011359C PK profile (for dose escalation), including area under the concentrationtime curve (AUC), maximum serum concentration observed postdose (C_{max}), minimum serum concentration observed postdose (C_{min}), and terminal half-life (t_{1/2}).
- Serum titers of anti-MSB0011359C antibodies.
- · BOR according to RECIST 1.1 per investigator assessments.

The secondary endpoints for the expansion part of the trial are:

- BOR according to RECIST 1.1 as adjudicated by the IRC
- BOR according to RECIST 1.1 per investigator assessments
- Duration of response according to RECIST 1.1 as adjudicated by the IRC
- Disease control rate according to RECIST 1.1 as adjudicated by the IRC
- PFS time according to RECIST 1.1 as adjudicated by the IRC
- OS time.

N/V

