8.5.3 Analysis of Secondary Endpoints

8.5.3.1 Efficacy Parameters

Clinical efficacy parameters will be analyzed descriptively in the full analysis set.

CONFIDENTIAL INFORMATION

Does escalation

For the dose escalation part of the trial, the secondary efficacy endpoint is BOR according to RECIST 1.1 per investigator assessment. For a BOR of PR or CR, confirmation of the response according to RECIST 1.1 (Eisenhauer 2009) will be required. The response at each scheduled tumor assessment and the BOR will be listed for each subject. The ORR, defined as the proportion of subjects with BOR of PR or CR, will be tabulated by dose level.

Dose expansion

For the dose expansion part of the trial, the primary secondary efficacy endpoint is confirmed BOR according to RECIST 1.1 as adjudicated by the IRC (Section 2.2.2) for the GC, ESCC and BTC cohorts.

For a BOR of PR or CR, confirmation of the response according to RECIST 1.1 (Eisenhauer 2009) will be required for the final analysis for both escalation and expansion parts. The response at each scheduled tumor assessment and the BOR will be listed for each subject. The ORR and associated 95% CIs will be tabulated for each cohort.

The following secondary endpoints will also be reported:

- Duration of response according to RECIST 1.1 as adjudicated by the IRC will be defined as the time from first confirmed response until the first documented disease progression that is subsequently confirmed. It will be analyzed using Kaplan-Meier method. Subjects without an event at the analysis cut-off date will be censored on the date of the last tumor assessment.
 - Disease control rate, defined as the proportion of subjects with BOR of CR, PR, or SD with minimum duration of 12 weeks according to RECIST 1.1 as adjudicated by the IRC, will be tabulated within each expansion cohort.
 - PFS time according to RECIST 1.1 as adjudicated by the IRC
 - The PFS time is defined as the time (months) from first administration of trial drug to the first observation of radiological PD (as assessed by the IRC) or occurrence of death due to any cause. PFS will be presented in listings and analyzed using the Kaplan-Meier method in GC, ESCC and BTC cohorts separately if the cohort enrolls the full planned number of subjects. The detailed censoring rules will be provided in the SAP.

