6.1 Decision after discontinuation of NSCLC and BTC trials

The data review outcome from the 3 randomized controlled studies in NSCLC and BTC (MS200647-0005, MS200647-0037, MS200647_0055) appears to indicate, consistently across 2 indications, either poorer observed hazard ratios for PFS and OS in the experimental arms with bintrafusp alfa or low likelihood for bintrafusp alfa to add benefits compared to standard of care. Based on this, the decision was made to not perform any final analysis after the final database lock. The study results have been described in the CSR approved on 31 March 2020 (cut-off date: 24th August 2018) and on CSR addendum approved on 25 March 2021 (cut-off date: 15th May 2020).

7 Changes to the Planned Analyses in the Clinical Study Protocol

There will be no final analysis after the final database lock.

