14.1.2 Best Overall Response According to RECIST 1.1 as Adjudicated by the IRC

The confirmed BOR according to RECIST 1.1 as adjudicated by IRC will be assessed based on reported overall responses at different evaluation time points from the start date until documented disease progression, according to the following rules:

- CR = at least two determinations of CR at least 4 weeks apart and before progression
- PR = at least two determinations of PR at least 4 weeks apart and before progression (and not qualifying for a CR)
- SD = at least one SD assessment (or better) \geq 6 weeks after start date and before progression (and not qualifying for CR or PR)
- Non-CR/Non-PD = at least one Non-CR/Non-PD assessment ≥ 6 weeks after start date and before progression with no measurable disease and does not meet criteria of CR
- PD = progression \leq 12 weeks after start date (and not qualifying for CR, PR or SD)

• ND = at least one ND assessment

The following rule will additionally be applied regarding derivation of BOR:

• Participants who miss the first two post-baseline tumor evaluations and subsequently are observed to have PD will be assigned a not-evaluable BOR (NE) (i.e. tumor assessment of PD is >12 weeks after start date and there is no tumor assessment in between).

When evaluating OR, both CR and PR must be confirmed by repeat assessments performed no less than 4 weeks after the criteria for response are first met. It is reasonable to consider a participant with time point response of PR-SD-PR, PR-NE-PR or CR-NE-CR as a confirmed response as long as the second CR or PR is more than 28 days away from the first time point.

The confirmed and unconfirmed objective response rate (ORR) will be calculated with a two-sided 95% CI using the Clopper-Pearson method (exact CI for a binomial proportion as computed by default by the FREQ procedure using the EXACT option).

As tumor lesions are evaluated by the IRC, it may happen that the independent reviewer disagrees with the investigator and does not assess any tumors as "measurable" at screening. In that case, the BOR could be rated as "non-CR/non-PD" (if no "CR" or "PD" are previously reported).

If the IRC is not able to identify any disease at baseline (target or non-target lesions), the BOR may be rated as "No Disease" (ND).

The following analyses will be performed:

- Number and percentage of participants with confirmed and unconfirmed BOR of CR, PR, SD, PD, and NE

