- Number and percentage of participants with confirmed and unconfirmed ORR with a twosided 95% CI
- Number and percentage of participants with confirmed and unconfirmed DCR with a twosided 95% CI
- Spider graph of individual percentage of change in the sum of diameter since baseline
- Waterfall graph of the change in the sum of diameters between baseline and the best post-baseline assessment (i.e. minimum change since baseline)

Listing of tumor assessment: participant identifier, age, sex, MSI status, PD-L1 expression, date of death when death occurs, unconfirmed and confirmed BOR, visit, date(s) of imaging, description of target lesions (size, site, type, method, response), non-target lesions (status, site, type, method, response), and new lesions (site, type, method), sum of lesion diameters, percent change in target lesions at baseline, and overall response, sorted by dose level/cohort, participant identifier, and visit.

In addition, a listing presenting responses (CR, PR) occurring after a first progression will also be provided including: participant identifier, age, sex, MSI status, PD-L1 expression, date of start of subsequent therapy, unconfirmed and confirmed BOR, visit, date(s) of imaging, sum of lesion

diameters, percent change in target lesions from baseline, overall response and flag for response after progression, sorted by dose level/cohort, participant identifier, and visit.

When BOR as adjudicated by IRC and investigator assessment are both available, a listing of inconsistencies will be provided.

Listings of efficacy assessments for both Investigator and IRC assessment will also be provided including: cohort, participant identifier, age, sex, MSI status, PD-L1 expression, date of first study treatment, treatment duration, cBOR, PFS, time to response, DR and OS. Efficacy assessments will be given for both investigator and IRC. Subjects with treatment ongoing or response ongoing will be flagged.

14.2 **Duration of Response**

Duration of Response (DR) measured from the time measurement criteria are first met for CR/PR until the first date of PD or death due to any cause within 84 days (12 weeks) or last tumor assessment if death occurred during the treatment period, or within 168 days (24 weeks) of last tumor assessment if death occurred during the follow-up period.

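### The SAP drops the protocol's 12-week minimum from the IRC disease control rate without declaring the change, so the reported rate can only equal or exceed the protocol's endpoint

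*SAP*

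**What the plan says.** **Protocol.** Section 8.3.2 lists, among the secondary endpoints of the expansion part, "Disease control rate according to RECIST 1.1 as adjudicated by the IRC". Section 8.5.3.1 gives the definition: "Disease control rate, defined as the proportion of subjects with BOR of CR, PR, or SD with minimum duration of 12 weeks", IRC-adjudicated and tabulated within each expansion cohort.

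**SAP definition.** Section 14.1 reads: "Disease Control Rate (DCR) is defined as the proportion of participants with BOR according to evaluation criteria of CR, PR, or SD". It gives no duration. It then adds: "For RECIST 1.1 as adjudicated by IRC, non-CR/non-PD will also be considered in DCR evaluation".

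**SAP rule for SD.** In 14.1.2, confirmed SD by IRC needs one assessment of SD or better, at or beyond "6 weeks after start date and before progression (and not qualifying for CR or PR"). PD becomes the BOR only when the subject does not already qualify for CR, PR or SD.

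**SAP outputs.** Section 14.1.2 plans "Number and percentage of participants with confirmed and unconfirmed DCR" with 95% confidence intervals. For the unconfirmed version, 14.1 says: "The unconfirmed BOR will be defined by the best overall response reached by the participant during this period". No minimum time is attached to SD there.

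**SAP declaration of changes.** Section 7 contains one item: "There will be no final analysis after the final database lock". Section 7.1 deals only with COVID-19. Section 4, which lists the analyses dropped and added for the CSR addendum, does not mention DCR.

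**The concern.** The protocol and the SAP use the same name for two different quantities. The protocol version asks for disease control that lasts. The SAP version can be met by one scan at about 6 weeks. Both SAP changes, removing the minimum and admitting non-CR/non-PD, can only keep the numerator the same or enlarge it.

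The SAP governs the CSR addendum. It re-describes IRC BOR because changes were seen in the gastric cohort, tabulates DCR, and says its analyses may go into submissions or manuscripts. A reader who sees a DCR table, and who finds in SAP Section 5 a pointer back to the protocol for endpoints, would take the figure to be the protocol's secondary endpoint.

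**Working it through.** The documents give no DCR value, assumption or DCR-based sample size, so there is no stated figure to reproduce. The check compares the rules and applies them to the scan calendar.

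**Inputs**
- Scans at Week 7 (Day 43) and every 6 weeks after that (next Day 85), with a window of 5 days before dosing: Protocol 7.1.2.2 and Table 2.
- Minimum duration of 12 weeks = 84 days: Protocol 8.5.3.1.
- SD cut-off of 6 weeks = 42 days: SAP 14.1.2.
- Default day count, stop minus start plus 1: SAP 9.4.
- Planned sizes: 30 each for GC and ESCC; BTC 30, rising to at most 100 if 5 or more of the first 20 respond; HCC 9 (Protocol Synopsis).

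**Step 1. Does one on-schedule scan give SD under the SAP?** Day 43 is 43 − 1 = 42 elapsed days, which meets the 6-week cut-off. Yes.

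**Step 2. Can that subject progress before 12 weeks and still count?** Elapsed days = study day − 1. The SAP 9.4 count equals the study day.

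| PD on | Elapsed days | SAP 9.4 count | 84 days reached? |
|---|---|---|---|
| Day 80 | 79 | 80 | No, under either count |
| Day 83 | 82 | 83 | No, under either count |
| Day 84 | 83 | 84 | Only with +1 |
| Day 85 | 84 | 85 | Yes, under both |

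SD on Day 43 followed by PD on Days 80-83 remains SD in the SAP and counts in DCR. It fails the protocol condition under both day counts. A subject with SD on Day 43 and no later scan also counts in the SAP, although 12 weeks of SD was never observed.

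**Step 3. How much depends on the start of the clock?** Neither document says where SD duration starts or ends. From first dose, 12 weeks is reached on Day 85. From a first SD scan on Day 43, it is reached on Day 43 + 84 = Day 127. The second convention would remove more subjects.

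**Step 4. Does another SAP section restore the minimum?** No. The 12-week figures in 14.1.1 and 14.1.2 define when PD or NE is the BOR. The 84-day figures in 14.2 and 14.3 govern duration of response and PFS.

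**Step 5. Size per subject.** 1/30 = 3.3 points; 1/100 = 1.0 point; 1/9 = 11.1 points in HCC.

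**Step 6. Illustration on assumed counts, n = 30, exact (Clopper-Pearson) 95% CI.** Suppose the SAP rule counts 15 subjects.

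| Subjects failing the 12-week rule | DCR under the protocol rule | 95% CI |
|---|---|---|
| 0 | 15/30 = 50.0% | 31.3 to 68.7 |
| 1 | 14/30 = 46.7% | 28.3 to 65.7 |
| 3 | 12/30 = 40.0% | 22.7 to 59.4 |

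**The case against.** Several points can fairly be made for the plan.

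- **SAP Section 5 refers to the protocol for endpoints.** True, but 14.1 then gives its own operative definition, and that is what would be programmed. The pointer makes the mismatch harder to notice.
- **The change may have been declared in an earlier plan.** This SAP serves the addendum. The main CSR was approved on 31 March 2020, before version 1.0 of this SAP (29 September 2020), so the definition used there cannot be seen. This stands as a limit on scope: the finding covers the addendum only.
- **The 6-week SD rule contradicts nothing.** Correct. The protocol requires confirmation only for CR and PR. The rule matters here only because it does not supply the missing 12 weeks.
- **The protocol wording is ambiguous.** The 12-week phrase could attach to SD alone or to all three categories. The SAP has no minimum under either reading, and the wider reading would make the gap equal or larger.
- **Non-CR/non-PD is mostly operational.** Eligibility requires measurable disease, so the category arises only when the IRC sees no measurable lesion at screening. That makes it a small addition, but it is still outside the protocol definition.
- **The impact is limited.** DCR is descriptive, the study endpoints are not tested, the BTC enrolment rule uses response, and listed scan dates allow recalculation. If the clock starts at first dose, PD on the scheduled Day 85 scan reaches 12 weeks, so only early or unscheduled progression, or no later scan, creates a difference. All of this stands and limits the severity.

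**Conclusion.** The concern holds. For the CSR addendum, the SAP replaces the protocol's IRC DCR with a quantity that has no 12-week minimum, adds non-CR/non-PD, and declares neither in Section 7. The reported rate can only equal or exceed the protocol's.

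The size is 3.3 points per affected subject at n = 30 and 1.0 at n = 100. The number affected is unknown, and the illustrated falls from 50.0% to 46.7% or 40.0% rest on assumed counts. The Days 80-83 example does not depend on the day-count convention. With duration counted from the first SD scan, it fails by a wider margin.

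This should be fixed because a named secondary endpoint has changed in one direction without being declared. It does not affect any decision made in the trial.

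**What to change.** - In SAP 14.1, restore the 12-week minimum for the IRC DCR and say whether it applies to SD only.
- State how SD duration is measured: start (first dose or first SD scan); end (PD or last evaluable non-PD scan, including when no later scan exists); day count (elapsed, or the +1 day of SAP 9.4); and any allowance for the scan window.
- The data cut-off was 15 May 2020 and the addendum was approved on 25 March 2021, so label any convention chosen now as post hoc. Reporting both start points would show how much the choice matters.
- Label any DCR without the 12-week condition, including the unconfirmed one, as supplementary.
- Declare in Section 7 the non-CR/non-PD addition and any departure that is kept.

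**Cost.** SAP wording and one relabelled or supplementary IRC DCR table, built from imaging dates and responses that the SAP already lists. No new data are needed. The reported DCR may be lower.

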14.1.1 Best Overall Response According to RECIST 1.1 as Assessed by Investigator

The confirmed BOR according to RECIST 1.1 as assessed by investigator will be based on reported overall responses at different evaluation time points from the start date until documented disease progression, according to the following rules:

- CR = at least two determinations of CR at least 4 weeks apart and before progression
- PR = at least two determinations of PR at least 4 weeks apart and before progression (and not qualifying for a CR)
- SD = at least one SD assessment (or better) \geq 6 weeks after start date and before progression (and not qualifying for CR or PR).
- PD = progression \leq 12 weeks after start date (and not qualifying for CR, PR or SD).

The following rule will additionally be applied regarding derivation of BOR:

- Participants who miss the first two post-baseline tumor evaluations and subsequently are observed to have PD will be assigned a not-evaluable BOR (NE) (i.e. tumor assessment of PD is >12 weeks after start date and there is no tumor assessment in between).
- When evaluating OR, both CR and PR must be confirmed by repeat assessments performed no less than 4 weeks after the criteria for response are first met. It is reasonable to consider a participant with time point response of PR-SD-PR, PR-NE-PR or CR-NE-CR as a confirmed response as long as the second CR or PR is more than 28 days away from the first time point.

The individual percentage of change in the sum of diameter since baseline will be displayed over time per dose level/cohort on a spider plot, together with the first occurrence of new lesion and participant off treatment.

A listing will present the tumor assessment and overall response per RECIST 1.1 as assessed by the investigator including: dose level/cohort, participant identifier, age, sex, date of start of subsequent therapy, MSI status, PD-L1 expression, date of death when death occurs, confirmed BOR, visit, date(s) of imaging, description of target lesions (size, site, type, method, response), non-target lesions (status, site, type, method, response), new lesions (site, type, method), sum of lesion diameters, percent change in target lesions from baseline, and overall response, sorted by dose level/cohort, participant identifier, and visit.

In addition, a listing presenting responses (CR, PR) occurring after a first progression will also be provided for dose expansion cohorts including: dose level/cohort, subject identifier, age, sex, MSI status, PD-L1 expression, unconfirmed and confirmed BOR, date of start of subsequent anti-cancer therapy, visit, date(s) of imaging, sum of lesion diameters, percent change in target lesions from baseline, overall response, and flag for response after progression, sorted by dose level/cohort, subject identifier, and visit.

14.1.2 Best Overall Response According to RECIST 1.1 as Adjudicated by the IRC

The confirmed BOR according to RECIST 1.1 as adjudicated by IRC will be assessed based on reported overall responses at different evaluation time points from the start date until documented disease progression, according to the following rules:

- CR = at least two determinations of CR at least 4 weeks apart and before progression
- PR = at least two determinations of PR at least 4 weeks apart and before progression (and not qualifying for a CR)
- SD = at least one SD assessment (or better) \geq 6 weeks after start date and before progression (and not qualifying for CR or PR)
- Non-CR/Non-PD = at least one Non-CR/Non-PD assessment ≥ 6 weeks after start date and before progression with no measurable disease and does not meet criteria of CR
- PD = progression \leq 12 weeks after start date (and not qualifying for CR, PR or SD)

• ND = at least one ND assessment

The following rule will additionally be applied regarding derivation of BOR:

• Participants who miss the first two post-baseline tumor evaluations and subsequently are observed to have PD will be assigned a not-evaluable BOR (NE) (i.e. tumor assessment of PD is >12 weeks after start date and there is no tumor assessment in between).

When evaluating OR, both CR and PR must be confirmed by repeat assessments performed no less than 4 weeks after the criteria for response are first met. It is reasonable to consider a participant with time point response of PR-SD-PR, PR-NE-PR or CR-NE-CR as a confirmed response as long as the second CR or PR is more than 28 days away from the first time point.

The confirmed and unconfirmed objective response rate (ORR) will be calculated with a two-sided 95% CI using the Clopper-Pearson method (exact CI for a binomial proportion as computed by default by the FREQ procedure using the EXACT option).

As tumor lesions are evaluated by the IRC, it may happen that the independent reviewer disagrees with the investigator and does not assess any tumors as "measurable" at screening. In that case, the BOR could be rated as "non-CR/non-PD" (if no "CR" or "PD" are previously reported).

If the IRC is not able to identify any disease at baseline (target or non-target lesions), the BOR may be rated as "No Disease" (ND).

The following analyses will be performed:

- Number and percentage of participants with confirmed and unconfirmed BOR of CR, PR, SD, PD, and NE
- Number and percentage of participants with confirmed and unconfirmed ORR with a twosided 95% CI
- Number and percentage of participants with confirmed and unconfirmed DCR with a twosided 95% CI
- Spider graph of individual percentage of change in the sum of diameter since baseline
- Waterfall graph of the change in the sum of diameters between baseline and the best post-baseline assessment (i.e. minimum change since baseline)

Listing of tumor assessment: participant identifier, age, sex, MSI status, PD-L1 expression, date of death when death occurs, unconfirmed and confirmed BOR, visit, date(s) of imaging, description of target lesions (size, site, type, method, response), non-target lesions (status, site, type, method, response), and new lesions (site, type, method), sum of lesion diameters, percent change in target lesions at baseline, and overall response, sorted by dose level/cohort, participant identifier, and visit.

In addition, a listing presenting responses (CR, PR) occurring after a first progression will also be provided including: participant identifier, age, sex, MSI status, PD-L1 expression, date of start of subsequent therapy, unconfirmed and confirmed BOR, visit, date(s) of imaging, sum of lesion

diameters, percent change in target lesions from baseline, overall response and flag for response after progression, sorted by dose level/cohort, participant identifier, and visit.

When BOR as adjudicated by IRC and investigator assessment are both available, a listing of inconsistencies will be provided.

Listings of efficacy assessments for both Investigator and IRC assessment will also be provided including: cohort, participant identifier, age, sex, MSI status, PD-L1 expression, date of first study treatment, treatment duration, cBOR, PFS, time to response, DR and OS. Efficacy assessments will be given for both investigator and IRC. Subjects with treatment ongoing or response ongoing will be flagged.

14.2 **Duration of Response**

Duration of Response (DR) measured from the time measurement criteria are first met for CR/PR until the first date of PD or death due to any cause within 84 days (12 weeks) or last tumor assessment if death occurred during the treatment period, or within 168 days (24 weeks) of last tumor assessment if death occurred during the follow-up period.

The analysis of DR will be performed using confirmed CR/PR according to RECIST 1.1 as measured by the investigator. For dose expansion participants (excluding HCC as there is no responder), analysis of DR according to RECIST 1.1 as measured by the IRC will also be performed.

DR will be censored in the following scenarios:

- Participants who do not experience an event (PD or death) will be right-censored on the date of their last evaluable (non-missing and non "Not Evaluable") tumor assessment.
- Participants who start new anti-cancer treatment prior to an event will be censored on the date of the last evaluable tumor assessment before anti-cancer therapy is given.
- Participants with an event after two or more subsequent missing response assessments (i.e. 2 times the scheduled time interval between two subsequent response assessments) will be censored on the date of the last evaluable (non-missing and non "Not Evaluable") tumor assessment.
 - Note: 2 times the scheduled time interval means 84 days during the treatment period and 168 days during the follow-up period (for participants who ended the treatment not for progression).
- Participants who do not have a baseline tumor assessment or who do not have any post-baseline tumor assessments will be censored on the date of first dose unless death occurred on or before the time of the second planned tumor assessment in which case the death will be considered an event.

 $DR = (date \ of \ PD \ or \ death/censoring - date \ of \ objective \ response + 1)/30.4375 \ (months).$

The analysis of DR will be performed with a Kaplan-Meier method (product-limit estimates) and a summary of associated statistics will be presented including corresponding two-sided 95% CIs. The CIs for the median will be calculated according to Brookmeyer and Crowley (1982) and CIs for the survival function estimates at month 3, 6, 12, 18, 24, 36, and 48 will be derived using the log-log transformation according to Kalbfleisch and Prentice (1980) (CONFTYPE=loglog default option in SAS PROC LIFETEST). The estimate of standard error will be computed using Greenwood's formula. DR rates with their CI at 3, 6, 9, 12, 18, 24, 36, and 48 months will be presented, as well as the number of participants at risk and failed.

The time and duration of response per participant will be displayed in a swimmer graph.

Listing will be provided with the following information: dose level/cohort, participant identifier, age, sex, MSI status, PD-L1 expression, date of first response, date of first PD or death, duration of response, and censoring reason.

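### The confirmed-PR rule in SAP 14.1.1 and 14.1.2 does not say that a CR confirms an earlier PR; read literally, a single PR followed by a single CR is scored SD

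*SAP*

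**What the plan says.** SAP 14.1 says that confirmed BOR must meet the confirmation rules in the sections that follow, so the bullets in 14.1.1 (investigator) and 14.1.2 (IRC) are the operative derivation. The CR, PR and SD bullets are the same in both sections:

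- Complete response: "CR = at least two determinations of CR at least 4 weeks apart and before progression".
- Partial response: "PR = at least two determinations of PR at least 4 weeks apart and before progression (and not qualifying for a CR").
- Stable disease: "SD = at least one SD assessment (or better") from 6 weeks after the start date and before progression, if neither CR nor PR is met.

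Both sections then add text on objective response, which times the repeat scan from the first sign of response ("When evaluating OR, both CR and PR must be confirmed by repeat assessments performed no less than 4 weeks after the criteria for response are" …). Some interrupted sequences are accepted: "It is reasonable to consider a participant with time point response of PR-SD-PR, PR-NE-PR or CR-NE-CR as a confirmed response". The proviso on timing is worded "as long as the second CR or PR is more than 28 days away from the first time point".

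SAP 14.2 states "The analysis of DR will be performed using confirmed CR/PR according to RECIST 1.1 as measured by the investigator", with an IRC version for the expansion cohorts other than HCC. SAP 15.1 and 15.2 define responders in the ADA and nAb listings by confirmed CR or PR. Protocol 8.5.3.1 makes IRC-confirmed BOR the leading efficacy endpoint for GC, ESCC and BTC. Protocol 7.3 and 8.5.3.1 ask for confirmation according to RECIST 1.1 without spelling out a PR followed by a CR.

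**The concern.** The SD bullet carries *or better*; the PR bullet does not. A scan showing CR therefore counts towards SD but, on the wording, not towards confirming a PR. The result runs against clinical sense: a subject who goes PR, SD, PR is a confirmed responder, while one who goes from PR to CR and has no further qualifying scan is not. The SAP gives no reason for the difference.

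At stake are confirmed ORR, the population for duration of response, confirmed BOR by ADA and nAb status (SAP 15.3), and the responder flag in the ADA and nAb listings. Only deepening responses can be lost, so the error has one direction. Even on the kinder reading, two programmers could class the same subject differently on the main efficacy measure.

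**Working it through.** The plan states no figure that depends on this rule, so there is none to reproduce. The check applies the bullets literally, then gives the size per subject.

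**Inputs.** Scans at Week 7 and every 6 weeks after that (Protocol 7.1.2.2), so Days 43, 85, 127 and so on. Consecutive scans are 85 − 43 = 42 days apart, which clears the 28-day minimum. Cohort sizes are 30 for GC and ESCC and up to 100 for BTC (Protocol Synopsis).

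**Step 1: one subject.** PR on Day 43, CR on Day 85, PD on Day 127.

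- CR bullet: one CR, two needed. Not met.
- PR bullet: one PR, two needed. Not met.
- SD bullet: the Day 85 scan is SD or better, after 6 weeks and before progression. Met.
- Result: SD.

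**Step 2: other sequences**, taking the bullets in the order CR, PR, SD, PD, first as written and then with PR read as PR or better.

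| Sequence | As written | PR or better |
|---|---|---|
| PR-CR; PR-CR-PD | SD | PR |
| SD-PR-CR; SD-PR-CR-PD | SD | PR |
| PR-NE-CR-PD; PR-SD-CR-PD | SD | PR |
| PR-PR-CR; PR-PR-CR-PD | PR | PR |
| PR-CR-CR-PD; PR-CR-NE-CR | CR | CR |
| PR-SD-PR; PR-NE-PR | PR | PR |
| CR-NE-CR | CR | CR |
| PR-PD; CR-PD | SD | SD |

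Only subjects with no two PRs and no two CRs at least 4 weeks apart change class. Genuinely unconfirmed responses (PR-PD, CR-PD) stay SD.

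**Step 3: size.** One subject is 1/30 = 3.3 points or 1/100 = 1.0 point of confirmed ORR. Exact (Clopper-Pearson) limits are the 0.025 quantile of Beta(x, n−x+1) and the 0.975 quantile of Beta(x+1, n−x). The responder counts below are assumed for illustration.

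| Cohort size | Subjects lost | As written | PR or better |
|---|---|---|---|
| 30 | 1 | 5/30 = 16.7% (5.6 to 34.7) | 6/30 = 20.0% (7.7 to 38.6) |
| 30 | 2 | 4/30 = 13.3% (3.8 to 30.7) | 6/30 = 20.0% (7.7 to 38.6) |
| 100 | 1 | 19/100 = 19.0% (11.8 to 28.1) | 20/100 = 20.0% (12.7 to 29.2) |

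The documents do not say how many subjects had such a sequence. With 0 to 2 per cohort assumed, the loss is 0 to 6.7 points at n=30 and 0 to 2.0 points at n=100.

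**The case against.** The strongest reply is that the SAP is ambiguous rather than wrong. The objective-response text asks for a repeat assessment at least 4 weeks later and speaks of a second CR or PR; a CR six weeks after a PR fits that description. The protocol's reference to RECIST 1.1 points to an outside standard that could settle the matter. The three named sequences are introduced as reasonable to accept, not as the only ones. Each has an interrupting SD or NE scan, and plain PR-PR is not listed either, so the absence of PR-CR does not show that it is excluded.

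That stands as far as it goes: misclassification is not certain. But none of this text says that a CR confirms an earlier PR. In each named sequence the second response is of the same category as the first, so the proviso need mean no more than that. SAP 14.1 sends the reader to the bullets, and the bullets give SD.

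The reply also limits the reach. Unconfirmed BOR, ORR and DCR are tabulated as well. The IRC listing in 14.1.2 shows every visit's response with both BORs, so an affected subject can be found. The cohorts are hypothesis-generating (Protocol Synopsis), and SAP 9.10 plans no tests on study endpoints. The illustrative intervals overlap heavily.

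**Conclusion.** The point holds in a narrow form. As written, the confirmed-PR bullet scores a single PR followed by a single CR as SD, and nothing else in the documents clearly overrides it. Any error lowers confirmed ORR, by 3.3 points per subject at n=30 or 1.0 point at n=100.

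A reader might infer more, and the documents do not support it:

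- *Every PR that deepens to CR is lost.* No. Two PRs at least 4 weeks apart before the CR give a confirmed PR, and two such CRs give a confirmed CR.
- *The subject vanishes from all response results.* No. Unconfirmed ORR keeps the subject, and so does the SAP's DCR, which counts SD.
- *The decision to enlarge the BTC cohort is affected.* No. Protocol 8.6 bases it on BOR without confirmation.
- *The reported ORR is known to be biased.* No. The documents show neither how the program classed such subjects nor whether there were any. The 0 to 2 per cohort is an assumption, and zero is possible.

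**What to change.** 1. In SAP 14.1.1 and 14.1.2, change the PR bullet to require at least two determinations of PR or better (PR or CR), leaving the 4-week gap, the before-progression condition and the exclusion of CR as they are. Name PR-CR and PR-NE-CR among the confirmed sequences. The new wording would also admit a CR followed by a PR, so state whether that order is meant to count.

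2. The text change alone alters no result. SAP version 2.0 (April 2022) follows the study report and its addendum, and SAP 6.1 cancels the final analysis. So query the existing listings for subjects with unconfirmed CR but confirmed SD, read each visit sequence (a lone CR before progression is correctly SD), and document how the program classed them. The main investigator listing in 14.1.1 does not carry unconfirmed BOR, so there look for confirmed SD with a CR at any visit before progression.

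3. If any such subject is found, correct confirmed BOR, ORR and DR together in the investigator and IRC outputs, with the ADA and nAb listings. SAP section 4 carries investigator BOR over from the study report without rerunning it. Correcting the addendum's investigator DR alone would put it on a different basis from that BOR.

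Cost: a few words in two sections, one listing query and, only if a case is found, a small re-derivation with a consistency check across the two reports.
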